## LIST OF ABBREVIATIONS AND RELEVANT DEFINITIONS

ABR	ABR form, General Assessment and Registration form, is the application form that is required for submission to the accredited Ethics Committee (In Dutch, ABR = Algemene Beoordeling en Registratie)
AE	Adverse Event
AR	Adverse Reaction
CA	Competent Authority
CCMO	Central Committee on Research Involving Human Subjects; in Dutch: Centrale Commissie Mensgebonden Onderzoek
CV	Curriculum Vitae
DSMB	Data Safety Monitoring Board
EU	European Union
EudraCT	European drug regulatory affairs Clinical Trials
GCP	Good Clinical Practice
IB	Investigator's Brochure
IC	Informed Consent
IMP	Investigational Medicinal Product
IMPD	Investigational Medicinal Product Dossier
METC	Medical research ethics committee (MREC); in Dutch: medisch ethische toetsing commissie (METC)
(S)AE	(Serious) Adverse Event
SPC	Summary of Product Characteristics (in Dutch: officiële productinformatie IB1-tekst)
Sponsor	The sponsor is the party that commissions the organisation or performance of the research, for example a pharmaceutical company, academic hospital, scientific organisation or investigator. A party that provides funding for a study but does not commission it is not regarded as the sponsor, but referred to as a subsidising party.
SUSAR	Suspected Unexpected Serious Adverse Reaction
Wbp	Personal Data Protection Act (in Dutch: Wet Bescherming Persoonsgegevens)
WMO	Medical Research Involving Human Subjects Act (in Dutch: Wet Medisch-wetenschappelijk Onderzoek met Mensen)

### **SUMMARY**

#### **Rationale:**

In type 2 diabetes (T2D), physical activity is an important modifiable risk factor of cardiovascular disease (CVD) and increased physical activity has been shown to positively impact upon cardiovascular health. Unfortunately (long-term) compliance to exercise programs in patients with T2D is poor. Light-intensity physical activity (LiPA); i.e., walking slowly, household activities or taking a flight of stairs) is also associated with a decreased CVD risk and can be more easily incorporated into daily life.

#### **Objective:**

To evaluate the effect of a LiPA intervention on arterial stiffness in individuals with T2D.

#### **Study design:**

This study is a single-blinded randomized controlled trial. The duration of the study is 12 months; a 6-month intervention with a 6 month follow-up period.

#### **Study population:**

160 men and women with T2D, aged 40-70 years old.

#### **Intervention:**

The intervention group will receive 4 workshops focussing on strategies to increase LiPA by reducing sedentary time. Participants in the intervention group will receive a feedback physical activity monitor worn on the wrist, data will be synchronized with a mobile phone app. The activity monitor will give real-time feedback on activity levels and will be used to set activity goals. Participants in the intervention group are encouraged to decrease their sedentary time with 10%. Participant in the control group will also receive 4 workshops focused on healthy lifestyle without an activity monitor.

#### **Main study parameters/endpoints:**

The primary outcome is pulse-wave velocity and carotid distensibility which will be determined with the use of applanation tonometry and arterial ultrasound. The effect of the intervention on the primary outcome PWV at month 6 will be analysed.

#### **Nature and extent of the burden and risks associated with participation, benefit and group relatedness:**

Study measurements of all participants will take place at baseline, month 3, month 6, and month 12 at the Maastricht UMC+. For the LiPA intervention only non-invasive low risk study procedures will be performed and the risk of any adverse events due to the different study procedures is low. A possible burden for the participant is the use of the activity monitors that participants are requested to wear continuously as a wristwatch.

### 1. INTRODUCTION AND RATIONALE

#### **Cardiovascular Disease and Arterial Stiffness**

Cardiovascular disease (CVD) is the major cause of morbidity and responsible for 75% of deaths in patients with type 2 diabetes (T2D). Besides atherothrombosis, also arteriosclerosis or increased arterial stiffness has been identified as an underlying cause of this increased CVD risk as increased arterial stiffness causes ischaemic heart disease, heart failure and stroke (1). Importantly, compared to individuals without T2D, patients with T2D are characterized by greater arterial stiffness (2, 3). Thereby, arterial stiffness is an important therapeutic target in T2D.

In this regard, we have shown previously that: 1) arterial stiffness is increased in patients with diabetes (4-6); 2) that there are complementary and additional roles for aortic and carotid arterial stiffness in the prediction of incidence of CVD (7) and, 3) that increased carotid arterial stiffness is independent from increased aortic arterial stiffness associated with incident stroke (8).

#### **Physical activity and Cardiovascular Health**

In T2D, physical activity is an important modifiable risk factor of CVD and increased physical activity has been shown to positively impact cardiovascular health (9). Unfortunately (long-term) compliance to exercise programs in patients with T2D is poor. These programs consist of a combination of aerobic and resistance training for several times a week and most participants quit exercising as soon as the (supervised) exercise intervention ends (10, 11). Most individuals with T2D have led a sedentary lifestyle over decades and they will generally find it difficult swiftly and consistently incorporate participation in exercise programs in their routine. Therefore, for patients with T2D the need to test alternative lifestyle changes that will be actually adopted by these individuals is compelling. From this perspective, it is important to shift our focus from exercise programs to physical activity of daily life or light-intensity physical activity ((LiPA); i.e., standing, walking slowly, household activities or taking a flight of stairs) which may play a crucial role to lower CVD in patients with T2D. Importantly, LiPA has been recognized as also having beneficial effects on cardiovascular health (12) and we have recently shown that high levels of sedentary time are associated with poor health and premature death independent of exercise (13, 14). Furthermore, we have also shown that replacement of sedentary time with LiPA lowers mortality risk (15). Thereby these results point at the importance of LiPA to improve (cardiovascular) health. Finally, LiPA can more easily be incorporated into daily life of sedentary individuals as it is made mainly of activities that are already part of everybody's routine (16-18).

### Physical Activity and Arterial Stiffness in Type 2 Diabetes

Data on the association between LiPA and arterial stiffness in T2D is currently scarce. The association between objectively measured LiPA and arterial stiffness (19-22) has been examined only in few observational studies and the conclusions of these studies are conflicting. In fact, one study showed that low LiPA was associated with increased arterial stiffness (19), but the same was not found in the others (20-22). The results of these studies are difficult to interpret and compare especially due to differences in study populations and the different physical activity monitor devices employed. Nevertheless, compelling data from intervention studies show aerobic exercise significantly decreases arterial stiffness, as estimated by aortic pulse wave velocity (PWV) (23). Interestingly, this review, where the results from a large number of studies were pooled, shows that the decrease in arterial stiffness was greater in individuals that had the stiffest arteries at the start of the interventions (23). This observation suggests that patients with T2D, in whom arterial stiffness is increased as compared to those individuals without T2D, will benefit most from increased (light) physical activity, when considering arterial stiffness as endpoint. Nevertheless, solid interventional data on the association between LiPA and arterial stiffness (in T2D) is currently lacking and this is the gap that we aim to fill.

Apart from increased CVD risk in T2D related to large blood vessel dysfunction (macrocirculation), there are also diseases that are related to small blood vessel dysfunction (microcirculation) (e.g. heart failure, (lacunar) stroke, depression, cognitive decline, retinopathy, chronic kidney disease, and neuropathy) (24-29).

We have shown recently that microvascular function is disturbed in prediabetes and T2D (30), and that microvascular dysfunction is associated with albuminuria and prevalent and incident depression (31, 32) indicating disturbance of renal and brain functions respectively. In large population studies, associations have been found between wider retinal venular diameters, a risk factor for CVD and diabetic retinopathy, and both low levels of physical activity and higher levels of sedentary behavior. Similar associations have been found in type 1 diabetic patients (10). In T2D, we recently demonstrated that higher levels of physical activity were associated with greater skin microvascular function (11. Sørensen BM, Houben AJ, Koster A, Berendschot TT, Schouten JS, Kroon AA, van der Kallen CJ, Henry RM, Savelberg HH, van Dongen MC, Eussen SJ, van der Berg JD, Schaper NC, Schram MT, Stehouwer CD. Higher levels of daily physical activity are associated with better skin microvascular function in type 2 diabetes: The Maastricht Study. Submitted 2018.). We expect that our randomized controlled trial to increase LiPA levels will result in a long-term change in physical activity behaviour and, improve microvascular function in patients with T2D

As far as the possibility to achieve a significant and long-term change of chronic sedentary behaviour is concerned, it has been shown that sedentary behaviour can be reduced (16-18, 33) and it is possible to increase LiPA by simply decreasing sedentary time (16-18). For example, a randomized controlled trial that focused on reducing TV viewing time showed a significant increase in total daily energy expenditure in those who just reduced their TV viewing time (17), whereas an Australian study showed that a brief intervention program to reduce sedentary behaviour in older adults successfully reduced sedentary time and thus showed its feasibility even in older sedentary individuals (16). Thereby, our randomized controlled trial to increase LiPA levels are expected to result in a long-term change in physical activity behaviour and, improve arterial stiffness in patients with T2D. In the end, this research will lead to a meaningful LiPA recommendation to decrease CVD risk in individuals with T2D.

During the past years, adipose tissue is being increasingly considered an “immune-metabolic-endocrine” organ. Many different types of immune cells accumulate in adipose tissue from obese individuals, such as macrophages and T-lymphocytes (34). Mechanistic studies in mice have shown that these cell types cause insulin resistance (35). Inflammatory processes in the adipose tissue influence the composition of immune cells in the circulation and consequently impact vascular complications and the development of type 2 diabetes (36, 37). We hypothesize that these disturbances in circulating immune cells are linked to the risk for micro- and macrovascular complications. Therefore, we aim to study whether lifestyle changes leads to quantitative and qualitative changes in circulating immune cells, and contribute to the reversal of the chronic inflammatory state that characterizes type 2 diabetes.

Hereto, we will measure circulating immune cells using flow cytometry from fresh whole blood (36). In addition, we will measure circulating cytokines to assess the activation state of immune cells, and store immune cells for functional tests.

## 2. OBJECTIVES

### Primary Hypothesis:

A LiPA intervention program based upon increasing LiPA by replacing sedentary time (approx. 1 hour) is effective in a) lowering arterial stiffness as estimated by aortic PWV and carotid distensibility and b) enhance microvascular function as estimated by retinal photos and skin heat-induced hyperemia in individuals with T2D.

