### **3. STUDY DESIGN**

This study is a single-blinded randomized controlled trial (enrollment via block randomization (block size of 4)). The duration of the study is 12 months; a 6-month intervention with a 6 month follow-up period to examine both the long-term health effects of the intervention as well as any long-term compliance to the intervention.

Study measurements of all participants will take place at baseline (month 1 (t = 0)), month 3 (t = 3), month 6 (t = 6), and month 12 (t = 12) at the Maastricht UMC+.

Participants in the intervention group will be instructed to increase their LiPA by decreasing sedentary time. Participants will follow 4 workshops in group sessions on strategies to change their behaviour and will receive a feedback physical activity monitor that will be worn continuously on the wrist and provide e-feedback on activity behaviour. During the COVID-19 crisis the workshops temporarily are offered online. The intervention procedures are described in more detail in section 5.

Participants in the control group will receive 4 workshops in group sessions on healthy lifestyle including information and strategies to increase LiPA and reduce sedentary time similar to the intervention group, but will not receive a feedback-activity monitor.

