## **5. TREATMENT OF SUBJECTS**

### **5.1 Investigational product/treatment**

#### Intervention group

The goal of the LiPA intervention program is to increase LiPA by reducing sedentary time by making use of a feedback activity monitor that is described in more detail below. The aim is to reduce sedentary time roughly by 10% as compared to baseline. Given that participants are sedentary for on average 9.3 hours (560 minutes) per day, participants are encouraged to decrease their sitting time by replacing approximately one hour per day of sitting time with LiPA activities. Sedentary behaviour, standing, and stepping time will be objectively measured making use of the activPAL® activity monitor that will be worn for 7 days continuously at baseline, month 3, month 6, and month 12. This device is blinded to the participant. The activPal® is a commercially available research tool ([www.paltech.plus.com](http://www.paltech.plus.com)). Data from the activPAL provide detailed and accurate information on the participants' sedentary, standing, and stepping time for each day.

Participants in the intervention group will be invited for a workshop, as a group session with approximately 20 participants. During this first workshop, extensive attention will be paid to what LiPA itself is, what the potential health benefits of LiPA are and how it can be incorporated into daily life and thus increased. Generic strategies to increase LiPA over the whole day will be discussed with participants. In month 2 and 3 of the trial, two additional group sessions will be organized during which progress will be discussed and if necessary further advise on how to increase LiPA. In the last month of the trial a final group session is planned which is followed by an unsupervised follow-up of 6 months. During the workshops topics related to a healthy lifestyle are being introduced. This information is based upon general healthy lifestyle guidelines, exercise guidelines and diabetes guidelines (please see below) In addition this will be an opportunity for participants to share their experiences.

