### Control group

Participants in the control group are, like the intervention group, invited for 4 workshops. These workshops are similar to the workshops of the intervention group, yet without the Fitbit inspire device. During the workshops topics related to a healthy lifestyle are being introduced. This information is based upon general healthy lifestyle guidelines, exercise guidelines and diabetes guidelines. Participants in the control group will not receive the e-feedback monitoring device. During the complete period of the study a manned help-desk is available for any questions by the participants about LiPA.

For safety reasons, for both the intervention and control group, a medical doctor (internist) is available (24/7) to discuss / advise on any alterations in the use of glucose lowering medication for both participant and general practitioners (or diabetes nurse practitioners). It can be expected that the most enthusiastic participants will experience alterations in their glucose levels which may require adjustment of their medication. Daily clinical care however remains the responsibility of the participant's own diabetes care provider either being the general practitioner or the diabetes nurse practitioner.

To note: the activPal ® ([www.Paltech.plus.com](http://www.Paltech.plus.com)) and Fitbit inspire (<https://www.fitbit.com/inspire>) are both commercially available research and consumer products and are incorporated into the trial as measurement tools but are themselves not part of the research aims of the current project. Both the ActivPal ® and the Fitbit inspire will be purchased by the investigational team from the respective companies.

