#### Workshop 2 – month 2 (duration 1 hour)

- physical activity and a healthy lifestyle in type 2 diabetes; therapeutic benefits
- reflection of participants on their LiPA levels
- group anonymized group feedback without comparison

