#### Workshop 3 – month 3 (duration 1 hour)

- group anonymized feedback without comparison
- group discussion on strategies to increase LiPA
- preparing for second part of the intervention without meetings or feedback at group level

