#### Workshop 4 – month 6 (duration 1 hour)

- looking back at the study
- group anonymized feedback without comparison
- long-term maintenance of LiPA healthy lifestyle

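### Do the missing comparator in the hypothesis and the unnamed source of control-group feedback leave the trial's contrast undefined?

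*Protocol*

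**What the plan says.** - **Objectives (section 2).** The primary hypothesis reads "A LiPA intervention program based upon increasing LiPA by replacing sedentary time (approx. 1 hour) is effective in a) lowering arterial stiffness". Neither it nor the primary objective has a comparator clause.
- **Study design (section 3).** Controls attend 4 lifestyle workshops, which the text describes as "including information and strategies to increase LiPA and reduce sedentary time similar to the intervention group, but will not receive a feedback-activity monitor".
- **Section 5.1, control group.** The workshops are described as similar to those of the intervention arm, and "Participants in the control group will not receive the e-feedback monitoring device".
- **Section 5.1, workshop overview, control group.** Workshop 1 has no feedback item. Workshop 2 lists "group anonymized group feedback without comparison", and workshops 3 and 4 list "group anonymized feedback without comparison". Workshop 3 also lists "preparing for second part of the intervention without meetings or feedback at group level". No data source is named.
- **Section 5.1, activPAL.** It is worn at baseline and months 3, 6 and 12, and "This device is blinded to the participant". A closing note says that the activPAL and the Fitbit "are incorporated into the trial as measurement tools but are themselves not part of the research aims of the current project".
- **Section 6.1.3, process evaluation.** Under the heading covering both arms, it asks how far the research nurse set goals together with the participant and gave feedback on general activity goals.
- **Sections 4.4 and 8.1.** The sample size contrast is intervention versus control. The primary analysis is intention-to-treat on PWV at month 6.

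**The concern.** Feedback on activity is the core of what the intervention arm receives on top of workshops. If controls also receive it, the reader needs to know what kind. There appear to be two candidates.

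- **activPAL summaries.** Controls would receive device-based group feedback at months 2 and 3, before the month-6 primary endpoint, taken from the device that measures a secondary outcome. The contrast would be individual electronic feedback against group device feedback.
- **Participants' own accounts.** The contrast would be device feedback against none.

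The protocol does not say which applies, so workshop groups could differ. Because the hypothesis is silent on the comparator, it could also be read as testing a LiPA programme against nothing, when controls are in fact taught LiPA strategies too. Two further wordings add to the doubt. The Summary describes the control workshops as healthy-lifestyle sessions without mentioning LiPA, and the note on devices calls the Fitbit a measurement tool although it delivers the intervention.

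**Working it through.** The plan states no figure on this point, so the check is a count and a comparison of texts.

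**1. Can the comparator be recovered?** Yes. Section 3 gives it in one sentence, section 5.1 repeats it and lists the workshop content, and section 4.4 names the two groups being compared. Only the comparator clause in section 2 is absent.

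**2. How often is control feedback listed?** Workshop 1: 0; workshops 2, 3 and 4: 1 each. Total 3 of 4. If control sessions hold about 20 people (stated only for the intervention arm, so an assumption here), 80 / 20 = 4 groups, and 4 × 3 = 12 sessions carry the item.

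**3. Could the activPAL supply it?** Wear is at months 0, 3, 6 and 12. Recordings available:

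| Workshop | Before that month | Including that month |
|---|---|---|
| Month 2 | 1 | 1 |
| Month 3 | 1 | 2 |
| Month 6 | 2 | 3 |

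At month 2 only the baseline recording exists, so a level could be reported but no change. Section 5.1 calls the device blinded to participants and a measurement tool. Section 9.3 lists the standard check-up results returned to participants, and activPAL data are not among them. That list concerns clinical tests, so it supports the point without settling it.

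**4. Is there a source that needs no device?** Yes. Controls learn general goal setting at workshop 1 and reflect on their own LiPA at workshop 2, and section 6.1.3 describes nurse feedback on general activity goals in both arms. This fits the blinding statement as written.

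**5. Do the workshop 3 and workshop 4 lines conflict?** Workshop 3 prepares participants for a period without meetings or group feedback, and workshop 4 at month 6 has both. The natural reading is that the period is the interval between month 3 and the closing session. The intervention arm has a parallel item about continuing without phone calls.

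**6. How much do the arms share?** Control topics: 4 + 3 + 3 + 3 = 13. Intervention topics: 5 + 5 + 4 + 4 = 18. With control feedback treated as distinct from comparative feedback, 8 topics are shared: 8/13 = 62% and 8/18 = 44%. With the three feedback items counted as shared: 11/13 = 85% and 11/18 = 61%. The share depends on the classification, so it cannot measure dilution. On either count the intervention arm alone has the monitor, scheduled phone calls (2 in month 1 if bi-weekly means every two weeks, plus 1 each in months 2 and 3, so 4) and a longer first workshop (2 + 1 + 1 + 1 = 5 hours against 4).

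**7. What changes between the two readings?** Allocation, the month-6 endpoint, the 73 (raised to 80) per group, the significance level and the model are the same under both. Only the description of the control condition differs.

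**The case for a change.** The strongest case for acting is that intervention content belongs in a protocol and cannot be left to an analysis plan. The control lines say feedback rather than activity feedback, but the activity reading is a strong inference. At workshop 2 the item follows reflection on LiPA levels, and its no-comparison qualifier mirrors the comparative progress feedback in the intervention arm. Another team could not reproduce the control sessions exactly. A second component is also loose: section 6.1.3 lists collaborative goal setting for both arms, whereas the workshop overview gives individual goal setting to the intervention arm only. Finally, the hypothesis invites a broader conclusion than the design supports, since the trial estimates what the monitor and its accompanying support add to LiPA workshops.

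Much of this stands as description. The source is unstated, and the hypothesis is less precise than section 3. What does not stand is the step to a design flaw. The troublesome consequences all require the activPAL to be the source, which goes against the plain sense of section 5.1. Even so, this would be an unspecified procedure and not a contradiction, because blinded may mean only that the device shows nothing while worn. The Summary does not say that the control workshops exclude LiPA, and section 3 treats LiPA strategies as part of healthy lifestyle. Calling the Fitbit a measurement tool is loose wording, since the rest of section 5.1 makes its role clear.

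**Conclusion.** No change to the plan is needed. The comparator is defined in sections 3 and 5.1, and its absence from the hypothesis is a drafting omission. The feedback source at 3 of 4 control workshops is operational detail, of the kind a workshop script would hold, and the text already offers a reading that is consistent with the blinding of the activPAL. Those reporting the trial can describe the contrast correctly from section 3 and state how the control feedback was given.

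The randomised comparison of PWV at month 6 is sound under either reading, and no stated number or analysis depends on the answer. No effect on PWV, carotid distensibility or power is shown, and the documents contain no figure from which one could be derived. The conclusion rests on two readings: that control feedback draws on general goals and participants' own reflection, and that the workshop 3 wording refers to the interval before month 6. If activPAL summaries were used instead, the control condition would be more active and should be reported as such, but the comparison would still be a valid randomised one.
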